16.4.2 Aim 4 Study Objectives

Primary Objective (Aim 4):

To utilize longitudinal molecular (plasma and HME), transcriptomic, and microbial data over the first seven days of critical illness to identify novel longitudinal, trajectories-based phenotypes, to determine the prognostic value for short-term clinical outcomes (primary: in-hospital mortality; secondary: organ-failure free days).

Exploratory Objectives (Aim 4):

1. To utilize longitudinal molecular, transcriptomic, and microbial data over the course of critical illness to identify novel longitudinal, trajectories-based phenotypes, to determine the prognostic value for and long-term patient outcomes assessed at 3, 6 and 12 months via physical, cognitive, and mental health outcome measures.
2. To determine the biologic trajectories of novel molecular and transcriptional phenotypes of APS over time and whether phenotype resolution is associated with recovery (Recovery = survival; 1-item recovery question; WHODAS \leq baseline WHODAS), and compare their natural course to previously described phenotypes.

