8.1.1 Participant/surrogate interview

Attempts will be made to interview enrolled participants (or a surrogate) during the index hospitalization. The purpose of the interview (which may be performed with the participant's surrogate if the participant is unable to participate in the interview) is to obtain contact information (which has been demonstrated to improve cohort retention), to assess baseline health and health behaviors, to assess race/ethnicity and skin tone, to understand social drivers of disease at baseline, and to assess for preexisting comorbidities and frailty. Domains of data collection via interview include:

- Contact information of patient and family members
- Skin color (Monk skin tone scale)
- Self-assessment of overall health (5-point Likert scale from Health & Retirement Study)
- Smoking status (current/former/never; pack-years)
- Alcohol use (AUDIT-C)
- Health-related quality of life (EQ-5D-5L)
- Frailty (Clinical Frailty Scale)
- Functional Limitations (Katz ADL/Lawton IADL)
- Disability (WHODAS-12)
- Employment status (ICAP-Revised)
- Cognitive function (IQ-CODE)
- Social isolation (NHATS-6)
- Engagement with healthcare (National Health Interview and All of Us Surveys)
- Education (Health and Retirement Study)
- Housing instability (Council of State Governments)
- Current/former opioid misuse (ARDS Network Long Term Outcomes Study)

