9.2.2 Email/SMS/Telephone Surveys

Following the chart review at each follow-up time point (3, 6, and 12 months), patients who have provided consent for study participation themselves (not through a surrogate or via alteration), are not known to be dead and not in hospital will be sent a link by email or SMS (“text”) message to a REDCap survey. The survey will be available in English and Spanish.

Patients who do not complete the online survey, either due to no response or because they did not previously provide consent themselves for study participation, will be contacted by telephone by study personnel. During this phone contact, patients who had not provided consent for study participation themselves (that is, who had been participating via surrogate consent or alteration of informed consent) will be given an opportunity to consent for the study themselves (see section 13.2.4). After consent procedures, surveys for data collection will be administered over the phone. Only patients who provide consent for themselves will be asked long-term outcome survey questions. If the patient lacks capacity for consent at the 3-month phone call, and a surrogate is available, a limited battery of questions may be administered to the surrogate over the phone. Survey phone calls will be completed in English or Spanish.

For each survey completed, patients may be reimbursed by the local Clinical Center/site in compensation for their participation (suggested amount: \$40). Reimbursement may be provided by gift card, electronic gift card, cash, or ClinCard, as determined by the local Clinical Center/site.

Surveys will include the following assessment domains/measures:

1. Reconfirm Contact Info: Email, Cell Number (Telephone survey only)
2. Pregnancy status (not known to be pregnant vs known to be pregnant)
3. Health related quality of life (EQ5D-5L)
4. Mental health, PTSD (IES-6)

5. Mental health, anxiety/depression (HADS)
6. Feedback questions related to ImproveLTO core outcome set surveys [www.improveLTO.com]
7. Recovery from acute illness (1-item Recovery Question from Long-COVID COS)
8. Dyspnea/pulmonary function (mMRC dyspnea scale)
9. Frailty (Clinical frailty scale)
10. Functional limitations: Abridged I/ADL limitations (toileting, transferring, feeding, telephone, med management, financial management)
11. Disability (WHODAS 2.0, 12-item)
12. Cognitive decline (PROMIS Cognitive Function Short Form 8a, 8-item)

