- Cumulative IV Sedation ^f	X	X	X	X		
- Sedation/Delirium	X	X	X	X		
- Blood Products	X	X	X	X		
APS Classification	X	X	X	X		
Outcome Data						
- Mortality						X
- Discharge location					X	
- Organ Failures	X	X	X	X	X	X
- ECMO / Prone position						X

Table 4 Footnotes

- a. The data collection schedule of events displays the study days from which data will be collected. The collected data will reflect patient status on those study days. The data may be collected later in a respective fashion.
- b. Study Day 0 is anchored on when the first study-specific biospecimen is collected. The time of first biospecimen collection is termed Time 0 and denotes the time a patient is enrolled into the study. Per study eligibility criteria, enrollment must occur within 48 hours of meeting inclusion criteria.
- c. Informed consent for the main study is listed in this table as a Day 0 procedure because most participants are expected to have informed consent obtained on Day 0. However, patients who enter the protocol on Protocol B using alteration of informed consent procedures may have consent obtained on a later day.
- d. Informed consent for the long-term outcome in-person visits is a separate consent process from consent for the main study. Informed consent for long-term outcome visits is listed as a hospital discharge procedure in this table because this consent is anticipated to be completed prior to hospital discharge for many patients. However, this consent may be completed at any time prior to initiation of in-person long-term outcome visit study procedures, including after hospital discharge. Long-term outcome surveys, which do not require in-person visits, may be completed without separate consent for the in-person long-term visits.
- e. The participant/surrogate interview aims to obtain information about participants' pre-hospital/baseline health and can occur at any time during index hospitalization, with completion as soon as possible after enrollment preferred.
- f. Cumulative amounts of continuous IV administration of select sedation agents will be collected from Study Day -2 to 7.

Table 5. Schedule of Events: Timing of post-hospital study visits.

Event	Study Day window for completing Event, by time point		
	3-month	6-month	12-month
A. Events for all survivors			
Medical record review	Day 53-67	Day 143-157	Day 329-337
SMS/email survey invite	Day 68-70	Day 158-160	Day 338-340
SMS/email reminder 1	Day 75-77	Day 165-167	Day 345-347

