13.2.3 Rationale for two study protocols with different approaches to informed consent

A key objective of this study is to rigorously phenotype ARDS, pneumonia, and sepsis, among severely and critically ill patients throughout their entire course of illness, beginning immediately when a patient meets eligibility criteria through 12 months later. To achieve this objective, patients must be enrolled as early as possible in their course of illness. Early biospecimens are crucial for the objectives of the APS Consortium. Up to 75% of patients in the ICU experience delirium or altered mental status prohibiting their ability to provide informed consent.²⁶ Frequently, LARs for critically ill adults are not available to provide written informed consent for research participation in a timely fashion. For example, prior work has shown that at a publicly-funded hospital, 18% of eligible patients for ARDS clinical trials are not enrolled due to the patient not having capacity for consent and no LAR/surrogate being available.²⁷

An accompanying protocol (APS Study Protocol B – alteration protocol) will be used when consent for study participation cannot be obtained before study entry. These protocols are linked. Protocol B

describes minimal risk study procedures that may be completed with alteration of informed consent and no written informed consent for study participation. The minimal risk study procedures in Protocol B are identical to study procedures in Protocol A. Protocol B contains a subset of study procedures from Protocol A that are minimal risk.

An approach of using two protocols to enroll participants – one that governs consented patients (Protocol A) and one that governs patients participating under alteration of informed consent (Protocol B) – is being utilized to minimize selection bias that would occur if only patients who were able to immediately provide written informed consent were enrolled. Outlining minimal risk procedures from the APS Study schedule of events in a separate protocol (Protocol B) enables participants without consent to begin minimal risk study procedures using an alteration of informed consent process. Meanwhile, participants with consent completed may engage in all study procedures, including both minimal risk procedures and greater than minimal risk procedures.

Goals of the study team include:

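### Aim 4 sets the WHODAS part of recovery as no worse than baseline with no margin for measurement error, and compares a baseline that a surrogate may have answered with a self-reported follow-up

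*Protocol*

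**What the plan says.** The definition is in protocol 16.4.2, under the exploratory objectives of Aim 4. The second objective asks "whether phenotype resolution is associated with recovery (Recovery = survival; 1-item recovery question; WHODAS", and the parenthesis closes by requiring WHODAS to be less than or equal to baseline WHODAS. No margin is given. The three elements are separated by semicolons, without stating whether a patient must meet all of them or whether each is its own outcome.

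The two WHODAS measurements come from different places:

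- **Baseline.** The 12-item WHODAS is part of the in-hospital interview (8.1.1), "which may be performed with the participant's surrogate if the participant is unable to participate in the interview". Table 4, footnote e, describes this interview as covering pre-hospital health and says it "can occur at any time during index hospitalization, with completion as soon as possible after enrollment preferred".
- **Follow-up.** The 12-item WHODAS 2.0 is in the 3-, 6- and 12-month surveys (9.2.2). There, "Only patients who provide consent for themselves will be asked long-term outcome survey questions". The one exception is a limited set of questions that a surrogate may answer at the 3-month call if the patient lacks capacity. The text does not say whether WHODAS is in that set.

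Section 16.4.6 adds that Aim 4's long-term outcomes will be adjusted for measures of pre-illness health.

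**The concern.** Three features of the rule matter.

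1. **No tolerance for error.** Both scores carry measurement error. In a patient whose disability has not changed, the follow-up score is about as likely to land above baseline as below it, and every landing above counts as failure.
2. **Dependence on baseline level.** A patient observed at zero can only stay or rise, while one at the top of the scale can never fail. Regression to the mean works in the same direction between these extremes.
3. **Change of respondent.** If surrogates systematically see more or less disability than patients report, that difference enters the change score, but only for patients with a surrogate baseline.

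The third feature can bias the comparison as well as blur it. Section 13.2.2 names intubation, sedation and unresponsiveness as states in which a patient may be taken to lack capacity for consent. Surrogate baselines are therefore plausibly more common in ventilated or sedated patients, and that status may differ between phenotypes. Part of an observed association between phenotype resolution and recovery could then reflect who answered at baseline. The first two features would mainly dilute a real association, or tie it to prior disability.

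**Working it through.** The protocol states no figure for this definition, so there is nothing to reproduce. It gives no WHODAS reliability, error SD, distribution, share at zero, surrogate share or surrogate bias. **All of the following are assumptions:** a 0-48 sum score (higher is worse), independent rounded normal error with SD 1 to 5 points at each assessment, and three true-score distributions with means of about 6, 13 and 21. There are 400,000 simulated patients per setting, none with any true change.

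**Step 1. Closed form, same respondent.** With symmetric, unbiased error, P(follow-up > baseline) = (1 - P(tie))/2.

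| Exact ties | Not recovered |
|---|---|
| 0% | 50% |
| 10% | 45% |
| 20% | 40% |
| 30% | 35% |
| 50% | 25% |

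**Step 2. Simulation, same respondent, error SD 1 to 5.**

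| True-score distribution | Not recovered |
|---|---|
| Low (mean about 6) | 34-43% |
| Middle (about 13) | 36-46% |
| High (about 21) | 36-47% |

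**Step 3. Some patients score a stable zero.** If a share s truly scores 0 and answers 0 both times, the result is (1 - s) × [1 - Φ(0.5/(SD√2))]. At SD 3 the bracket is 1 - Φ(0.118) = 0.453, so s = 0.2 gives 0.8 × 0.453 = 36%. Over SD 1 to 5:

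- s = 20%: 29-38%
- s = 40%: 22-28%
- s = 60%: 15-19%

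**Step 4. Dependence on observed baseline, error SD 3.**

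| Distribution | Not recovered, baseline 0 | Not recovered, baseline 16 or more |
|---|---|---|
| Low | 58% | 34% |
| Middle | 72% | 37% |
| High | 86% | 40% |

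The 86% describes very few patients, because almost nobody in the high distribution is observed at zero. In the low distribution 21% are. The stable zeros of Step 3 are not in these figures and would lower the baseline-0 column.

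**Step 5. Systematic surrogate shift, error SD 3, every baseline by surrogate.** Without clipping at the scale ends, P = 1 - Φ((0.5 + b)/(3√2)), where b is the surrogate's overstatement of baseline disability.

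| b | Closed form | Simulation, three distributions |
|---|---|---|
| -4 | 79.5% | 68-79% |
| -2 | 63.8% | 56-64% |
| 0 | 45.3% | 42-45% |
| +2 | 27.8% | 27-28% |
| +4 | 14.4% | about 14% |

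**Step 6. Scale by the surrogate share.** Step 5 is the extreme in which all baselines are by surrogate. Between two phenotypes, the bias is the difference in surrogate share times the shift. A 2-point bias shifts the simulated result by about 15 points (low distribution: 56.3 - 41.7 = 14.6) to 19 points (high: 63.8 - 45.2 = 18.6). With an illustrative 20 to 30 percentage-point difference in surrogate share, the bias runs from 0.20 × 14.6 = 2.9 to 0.30 × 18.6 = 5.6, or about 3 to 6 percentage points.

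**Step 7. Effect of a margin, error SD 3, same respondent.** The stated rule gives 42-45% not recovered. If the rise must exceed 2 points the figure is 24-28%, if 4 points 11-14%, and if 5 points 7-10%. These margins are illustrative; the protocol offers none.

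**The case against.** The best case for leaving the text alone has four parts.

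- **The objective is exploratory.** Aim 4's primary outcome is in-hospital mortality, and 12.2.2 and 16.4.7 require a filed analysis plan before analysis. A margin or a respondent covariate could be added there. This limits the priority. But the protocol does not leave the threshold open; it writes one down without a margin.
- **Adjustment is already planned.** Section 16.4.6 adjusts for pre-illness health. That could lessen the dependence on baseline level. It does not undo misclassification at a zero-margin cut, and it does not address who answered.
- **Return to the pre-illness level is an ordinary meaning of recovery.** This stands. Because the rule is less than or equal, a patient who starts and ends at zero counts as recovered. The difficulty is noise around the cut, not the idea.
- **The respondent may already be recorded.** The case report forms are not shown, so the protocol does not establish that the field is missing. The request is therefore to confirm it.

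A reader might infer that surrogates often supply the baseline. Section 13.2.3 says "Up to 75% of patients in the ICU experience delirium or altered mental status prohibiting their ability to provide informed consent", but that concerns capacity to consent. The interview may take place at any time in the stay, and patients with a follow-up WHODAS survived, so many may have answered for themselves. The documents support only that a surrogate may have answered.

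**Conclusion.** The concern holds for the WHODAS component of an exploratory objective. As written, the rule has no tolerance for measurement error, depends on baseline level, and permits a surrogate baseline to be set against a self-reported follow-up. How the three components combine is also unstated; if all must be met, non-recovery can only be higher than on WHODAS alone.

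The mechanism is certain, but the size is not. Under the assumed error and distributions, about 34-47% of truly unchanged patients would be classed as not recovered with the same respondent, or about 15-38% if 20-60% score a stable zero. A surrogate bias moves this in either direction, in proportion to the surrogate share.

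Two stronger readings go too far. One is that a fixed 40% of unchanged patients are misclassified. That needs about 20% exact ties and unbiased error, and the protocol gives neither. The other is that the respondent effect exceeds the effects Aim 4 seeks. Section 16.4.8 states no effect size for recovery, and the large shifts in Step 5 apply only if every baseline is by surrogate.

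**What to change.** In 16.4.2, make the main analysis of this component follow-up WHODAS as a continuous or ordinal outcome, with death ranked worst, adjusted for baseline WHODAS and baseline respondent type (self or surrogate). This also fits the stated preference in 12.2.1 for methods that use the raw data fully. Make sure the baseline interview records who answered, since a later analysis plan cannot reliably reconstruct it.

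If a binary recovery is kept, make it secondary, prespecify a margin above baseline, and state whether survival, the 1-item question and WHODAS are joined or reported separately.

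The cost is a change of wording, confirmation of one field on the form, and the choice of a margin for the binary version. Asking patients again about pre-illness WHODAS at follow-up is not needed: it would add 12 items to an already long survey and bring recall error of its own.

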16.4.3 Aim 4 Study Population

All participants enrolled in the APS Consortium will be eligible to participate in Substudy D.

16.4.4 Aim 4 Study Design

Prospective molecular cohort study with scheduled blood and microbiome sampling during the index hospitalization and with longitudinal follow-up at 3, 6, and 12 months after critical illness.

16.4.5 Aim 4 Study Procedures

Clinical and molecular data generated in the previously described in Aims 1, 2, and 3 will be collated and standardized.

16.4.6 Aim 4 Data, Images, and Biospecimens Used from the APS Consortium

Clinical data including syndromic phenotype (ARDS, pneumonia, sepsis), presence/type of infection, risk factors for ARDS, demographic information, comorbidities, severity of illness, physiologic data, and outcomes (survival, duration of organ support) will be utilized from each participant's inpatient admission. Clinical laboratory values and treatments will also be collected. Long term outcomes including measures of functional status, quality of life, emotional health, cognitive performance, and respiratory symptoms at 3, 6, and 12 months will also be tested outcomes, and will be adjusted for metrics of pre-illness health. Images from the inpatient stay or the longitudinal 12 month visit will be utilized, and from longitudinal muscle ultrasound, will be used.

Biological samples will include the results from all assays performed on the plasma, host whole blood RNA expression, and pathogen and microbiome assessment from samples obtained on days 0, 2, 4, and 6, along with respiratory sample profiling (HME filter fluid proteins) obtained at intubation and day 6.

16.4.7 Aim 4 Statistical Analysis

It is recognized that methods for analysis continue to be developed and evaluated. A detailed SAP will be generated before analysis begins, in which we will specify the method considered optimal at the time or, if an optimal method cannot be easily determined, competing methods will be compared. The following sections outlines a general approach that might be expected undertaken for this aim.

16.4.7.1 Evaluate existing phenotypes

Initially, we propose that for each cohort, at each time point, we will take two complementary modelling approaches to identify classes and/or phenotypes: 1) latent class analysis (LCA); 2) parsimonious classifier model (or these will be substituted or augmented if comparable or better performing models are identified). To date, LCA has been the gold-standard algorithm to identify the molecular phenotypes at cross-sectional timepoints. However, LCA uses variables standardized and scaled to the distribution of each cohort / timepoint. Therefore, at later timepoints, as disease states resolve and/or therapies take effect, physiology will likely normalize, leading to a divergence in the statistical solution and biological signature captured by LCA. It is conceivable, that while LCA at later time points may identify two classes, their biological characteristics may differ from those identified at baseline, as overall distributions in the population changes. Thus, we currently propose to evaluate the temporal kinetics of the biological signature of the previously derived “molecular phenotypes”, defined as Hypoinflammatory and Hyperinflammatory phenotypes identified using LCA at enrollment. At each time point, we will fit a parsimonious logistic regression classifier model which, unlike LCA which uses z-score standardized variables, uses the original scales of protein biomarkers and clinical variables;⁷ therefore, it is more likely to capture the biological signatures that define the phenotypes.

The variables used to perform LCA will be similar to those used in our prior studies and include clinical variables and protein biomarkers. Non-normally distributed data will be log-transformed and continuous variables will be scaled using z-scoring using values specific to the study day. Outcome data and severity scores (e.g., APACHE and SOFA scores) will be excluded from the modelling. We will build a minimum of five models, comprising of 1 to 5 classes respectively. We will use fit statistics and the Vuong-Lo-Mendall-Rubin test to determine the best fitting model in each cohort at each timepoint. Once identified, we will use the highest probability generated by the best fitting model to assign class membership. We will use latent transition modelling to evaluate the temporal stability of the classes at sequential time points. To establish overlap with the baseline molecular phenotypes, we will use the parsimonious classifier models comprising of IL-8, protein C, and serum bicarbonate. We plan to use a probability of ≥ 0.5 to assign molecular phenotypes. We will perform mixed effect modeling assessing for overall group differences in parsimonious model probabilities over time between survivorship groups in each phenotype independently. We will perform unadjusted (main) and confounder-adjusted analysis of probabilities trajectories, to ascertain cluster association with outcomes.

For gene-based existing phenotypes, we will use repeated RNA-sequencing data to classify patients to the various phenotypes (SRS, MARS, etc.). We will use the probabilities of belonging to the phenotypes on each day to model for trajectories and use outcome data to evaluate the prognostic value of the changing probabilities and switching of phenotypes, adjusting the models for treatment such as corticosteroids.

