16.4.1 Aim 4 Background and Rationale

Molecularly-defined phenotypes with different predicted survival and differential response to multiple randomized therapies have been validated in multiple critical illness populations with APS.^{1,2,3} However, the vast majority of existing work has been performed using plasma protein and clinical phenotyping from only the earliest timepoint, and not considering the dynamic nature of class-defining markers over time. We hypothesize that the trajectory of molecular phenotypes have important prognostic information about patients' condition, and that the resolution of 'hyperinflammatory' phenotype will associate with improved survival. Furthermore, by considering new plasma proteomic features, transcriptomic features, and microbial data over time, we hypothesize that novel phenotypes with distinct biological dysregulation can be identified, which in turn may yield novel precision treatment paradigms for APS.

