16.4.9 Aim 4 Expected Output

The completion of these described study objectives will generate the following expected output:

- Evidence to accept or refute a state change from hyperinflammatory subphenotype to a less inflamed phenotype as a prognostic indicator, which can then be tested as a theragnostic marker in future trials
- Novel biologic subphenotypes that incorporate longitudinal data and more diverse data elements than currently exist, which may yield better tools for prediction of long-term health states
- Novel biologic subphenotypes that may demonstrate unique biology that is both identifiable and pharmacologically targetable

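### In Aim 4, if the Day 0 value that assigns the phenotype is also the baseline for change, regression to the mean can make resolution look prognostic when no patient changes

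*Protocol*

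**What the plan says.** Aim 4 hypothesizes (16.4.1) that "the resolution of 'hyperinflammatory' phenotype will associate with improved survival". An exploratory objective in 16.4.2 asks "whether phenotype resolution is associated with recovery". The first expected output in 16.4.9 is "Evidence to accept or refute a state change from hyperinflammatory subphenotype to a less inflamed phenotype as a prognostic indicator", to be carried into future trials as a theragnostic marker. Resolution has no operational definition beyond this.

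The analysis is in 16.4.7.1. The molecular phenotypes are "defined as Hypoinflammatory and Hyperinflammatory phenotypes identified using LCA at enrollment". A three-variable classifier (IL-8, protein C, bicarbonate) is then applied at each time point, and "We plan to use a probability of ≥ 0.5 to assign molecular phenotypes". The comparison is: "We will perform mixed effect modeling assessing for overall group differences in parsimonious model probabilities over time between survivorship groups in each phenotype independently". It is followed by: "We will perform unadjusted (main) and confounder-adjusted analysis of probabilities trajectories". For the gene-based phenotypes, a separate paragraph plans to "use outcome data to evaluate the prognostic value of the changing probabilities and switching of phenotypes", with adjustment for treatment.

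Two other places bear on this. Section 16.1.5 (Aim 1) says the hyper- and hypoinflammatory phenotypes will be identified with the published parsimonious models, with latent class analysis (LCA) as a secondary check. Section 16.4.7.2 gives the longitudinal models a random effect per participant and adds joint models for dropout.

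**The concern.** A single day's classifier value is the patient's underlying level plus day-to-day and assay variation. Selecting patients because that value was high on Day 0 also selects positive errors. The error is largest, on average, in patients whose underlying level is near or below the cut. They fall back most at the next measurement, and because their underlying level is lower they also die less often. Inside the Day 0 hyperinflammatory group, a fall therefore goes with survival although no patient's state has changed.

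The plan sets up this situation by working within enrollment phenotype and making the unadjusted comparison the main one. Nothing stated separates a patient's underlying level from change when change is related to outcome. At stake is the conclusion in 16.4.9: a statement about state change, offered as a basis for later trials, could rest on an association that selection alone produces.

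**Working it through.** **No figure to reproduce.** Aim 4 states no effect size, power or sample size for resolution. The nearest stated figure is in 16.1.8: about 450 hyperinflammatory patients of 1,500, which is 0.30 x 1,500 = 450 (25% gives 375).

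**Inputs from the Protocol.** Hyperinflammatory share 25-30% (16.1.8; 27.5% used). Mortality 30% (16.2.8). Patients with Day 6 molecular data 1,000-1,800 (16.4.8). Cut at probability 0.5 (16.4.7.1).

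**Assumptions not in the documents.** Single-sample reliability 0.8 (range 0.5-0.95), log odds ratio of death 0.7-1.0 per SD of true level, classifier slope 3 per SD, independent errors between days, two-sided alpha 0.05.

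**Model with no true change.** X_t = T + e_t at Days 0, 2 and 6, with T constant for each patient. Logit L_t = 3(X_t - c), probability P_t = expit(L_t), and c set so that 27.5% have P_0 of at least 0.5. Death depends on T only.

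**Mechanism.** L_6 - L_0 = 3(e_6 - e_0).
- In the whole cohort e_0 is independent of T, so change is unrelated to death.
- Among patients selected on X_0, e_0 and T are negatively correlated. Low T then goes with a larger fall and lower mortality.
- L_6 - L_2 = 3(e_6 - e_2) stays independent of T even after selection on Day 0.

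**Expected values** (reliability 0.8, log OR 1.0, selection on the classifier value). 31% of Day 0 hyperinflammatory patients drop below 0.5 by Day 6. The mean fall in probability is 0.177 in survivors and 0.106 in non-survivors, a difference of 0.071. Mortality is 39.0% below 0.5 and 57.0% still above it: OR = (0.390/0.610)/(0.570/0.430) = 0.48. Over reliability 0.5-0.95 and log OR 0.7-1.0 this OR runs from 0.48 to 0.61.

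**Rejection rates at nominal 5%** (N = 1,800, reliability 0.8, log OR 1.0), by the correlation between the Day 0 error of the score that assigns the phenotype and that of the classifier. The trajectory test is survivorship by time with a random intercept. The switch is P_6 below 0.5 among patients who are hyperinflammatory on Day 0.

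| Error correlation | Trajectory | Switch |
|---|---|---|
| 0 | 5.5% | 61% |
| 0.3 | 11% | 71% |
| 0.6 | 23% | 81% |
| 1.0 | 70% | 96% |

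Varying how strongly level drives death, and testing change from Day 0 to Day 6, the trajectory rate is about 58-96% at correlation 1.0, 23-47% at 0.6 and near 5% at 0.

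**Candidate repairs under the same null.**
- Logit change in all patients, no Day 0 restriction: 3-7%, also with unequal error between days.
- Day 0 selection, logit change from Day 2 to Day 6: 3-7%, also with unequal error.
- Adjusting for Day 0 level alone (N = 1,500, reliability 0.8): change 79.5%, switch 47.7%.
- Outcome on mean level plus change: 3.8-6.3% with equal error, but 28-60% if reliability is 0.85 then 0.75, and 77-99% if it is 0.9 then 0.7.

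**The case against.** **The phenotype is assigned by LCA at enrollment, not by the classifier.** Section 16.4.7.1 does say this, and the sentence with the 0.5 cut names no day. If the two scores shared no Day 0 error, the trajectory test would be close to nominal. This stands as a limit on the size. It does not remove the problem: 16.1.5 names the parsimonious classifier as the means of identification, and an LCA that uses the same biomarkers from the same sample shares at least part of the error.

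**Switching is not planned in this way.** A reader might infer that the plan tests switching inside Day 0 hyperinflammatory patients. The text does not say so. Switching as a predictor is written for the gene-based phenotypes, with treatment adjustment and no Day 0 restriction. The switch figures apply only if 16.4.9 is answered by that route.

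**The quoted model may not test change.** If the overall group difference means a survivorship main effect, it compares level. That is valid, but it cannot support a claim about change of state. Nor should one say that the plan has no patient term at all: 16.4.7.2 has a participant random effect. The trajectory rates in the table include a random intercept, and it does not cure the bias.

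**A value below 0.5 on Day 6 does predict survival.** True: it carries information on level. As plain prediction that is sound. Reading it as change of state is not.

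**Other safeguards exist and the section is provisional.** Latent transition modelling is stated for class stability, with no link to outcome. Joint models address dropout. Section 12.2.5 asks that uncertainty in cluster membership be carried forward, which does not separate level from change. Section 16.4.7 calls the text a general approach ahead of a SAP, and this lowers the severity. But the within-phenotype comparison and the unadjusted main analysis are stated, and a SAP that follows them inherits the bias.

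**Conclusion.** The concern holds in conditional form. Where the Day 0 value that assigns the phenotype is also the baseline for change, the planned comparison can show resolution as prognostic with no change in any patient. The trajectory test is wrong in about 58-96% of no-change runs with fully shared error, 23-47% at correlation 0.6, and near 5% with none. A switch below 0.5 within Day 0 hyperinflammatory patients reflects underlying level in every case tried.

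A reader might infer that the analysis will nearly always give a false positive. The documents do not support that, because they name two ways of assigning the phenotype and the rate depends on which is used. The sizes also rest on assumed reliability, strength of the link between level and death, and independent errors between days. Death or discharge before Day 6 was not simulated.

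Severity is moderate. Resolution is an exploratory objective; the primary objective of Aim 4 concerns novel trajectory phenotypes and in-hospital mortality.

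**What to change.** In 16.4.7.1 and the Aim 4 SAP, test change on the classifier's logit scale in one of two ways:

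1. in all patients, without restriction to Day 0 class; or
2. within Day 0 phenotype, with change measured from Day 2 to Day 6, so that the selecting sample is not the baseline.

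Report switching across the 0.5 cut descriptively, and say which score assigns the enrollment phenotype (16.1.5 and 16.4.7.1 differ). Do not rely on adjustment for Day 0 level. Keep a model of outcome on mean level plus change as a sensitivity analysis only: it needs equal measurement error on the two days, and 16.4.7.1 itself expects distributions to shift as physiology normalises.

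The cost is wording; Day 0, 2 and 6 blood is already scheduled (Tables 7 and 9). The Day 2 to Day 6 version misses change before Day 2, uses only patients with both samples, and assumes that the Day 0 error does not persist to Day 2.
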